1.2 Background and Rationale

Differentiated thyroid cancer (DTC) is the most frequently diagnosed primary endocrine-related malignancy, accounting for 3.8% of all new cancer cases in US. The majority of cases are papillary and follicular and 10-year overall survival is excellent, exceeding 90%. (Clement 2015) Treatment for DTC consists of total or near-total thyroidectomy, followed by administration of radioactive iodine (I-131) for remnant ablation or residual disease. (Clement 2015)

I-131 has been used in therapy for well-differentiated thyroid cancer for over 50 years. The use of RAI is an essential adjuvant treatment strategy after thyroidectomy in patients with DTC. The 2009 ATA guidelines recommend I-131 ablation in high-risk patients and selected low-risk patients (1-4 cm thyroid cancer confined to thyroid and high-risk features predicting an intermediate to high-risk of recurrence or death from thyroid cancer) (Cooper 2009). The primary objectives of RAI treatment include eliminating residual normal and tumoral thyroid cells as the absence of normal residual

thyroid tissue improves the sensitivity of subsequent serum thyroglobulin levels as a tumor marker during follow-up for recurrence (Van Nostrand 2009). The eliminated normal residual thyroid tissue can no longer compete to take up a portion of administered RAI thus increasing sensitivity of detection of locoregional and/or metastatic disease on follow-up RAI whole body scans. Additionally, the absence of intense uptake in the thyroid bed that would otherwise obscure other foci of adjacent uptake allows post-treatment scans to reveal additional disease that was not previously identified.

RAI therapy is usually carried out with high doses of iodine-131, and, in cases of recurrent or progressive iodine-avid metastatic disease, is often repeated to get favorable response. RAI therapy is performed following either thyroid hormone withdrawal or preparation with recombinant human thyroid stimulating hormone (rhTSH) using whole-body and blood clearance studies. For successful remnant ablation in low-risk and high-risk patients, a minimum activity of 30-100 mCi/1.1-3.7GBq and 100-200mCi/3.7-74 GBq is recommended (Clement 2015, Cooper 2009)

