Treatment with I-131 can also result in disturbed nasolacrimal gland function and xerophthalmia resulting from inflammation of lacrimal gland. Recent studies have shown evidence of xerophthalmia in 16-33% of patients lasting for up to 2 years. (Van Nostrand 2009) A recent review reported that an abnormal Shirmer's test was found significantly more frequently in patients exposed to I-131 compared to unexposed patients. (Clement 2015) RAI uptake by nasolacrimal duct mucosa leads to subsequent inflammation, edema, and fibrosis and can be responsible for lacrimal duct obstruction and resulting chronic epiphora. (Fard-Esfahani 2014). Conjunctivitis has also been reported in 23% of patients. (Van Nostrand 2009)

Leukopenia, thrombocytopenia, and anemia are major risks of I-131 therapy. (Van Nostrand 2009) Of the known potential adverse events of I-131 therapies, bone marrow suppression has been considered the most important. (Bikas 2016) More than 20 publications have described bone marrow suppression secondary to I-131 therapy, though most are underpowered. Bone marrow suppression is mostly transient and results in a decreased in white blood cell and platelet count for up to 6-10 weeks. Total incidence is about 25% with leukocyte and platelet count nadirs 1-2 months after RAI administration (Fard-Esfahani 2014) Occasionally it results in increased susceptibility to infection or bleeding if the marrow dose exceeds about 200 cGy. (Fard-Esfahani 2014)

Of those patients receiving high-activity therapies, 38% have grade 1 bone marrow suppression as defined by the World Health Organization (WHO). Previous research has shown that even a single dose of RAI can cause changes in the peripheral CBC. (Padovani 2014) The degree to which an individual is affected is influenced by many factors including the patient's clearance rate, the total cumulative prescribed activity of I-131, the frequency of therapy and interval between treatments, the patient's bone marrow reserve and the degree to which bone metastases are present. Interpretation of the hematologic effects of RAI therapy is complicated by the fact that many patients who require high cumulative activities of RAI also receive external beam radiation therapy (EBRT) to treat metastatic lesions to the bone, which carries its own hematopoietic toxicity (Padovani 2014)

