First reported in 1963 by Haynie et al, transient leukopenia, anemia, and thrombocytopenia and occasional persistent anemia were noted after repeated RAI doses administered at 3-month intervals with traditional thyroid hormone (TH)

withdrawal. (Padovani 2014, Haynie 1963) More recent studies confirm what appear to be transient effects on blood counts measured in the first few weeks after RAI therapy, which some studies have shown to be less evident with an rhTSH preparation as compared to traditional TH withdrawal. To minimize BM suppression, Benua et al suggested not exceeding 200 cGy. (Van Nostrand 2009)

Tumor Derived Exosomes

Exosomes are small extra-cellular vesicles produced by all cells and present in almost all biological fluids including blood, urine, ascites, CSF, serum and plasma, and in the culture medium of cell cultures. (Whiteside 2016, Silva 2015) Currently exosomes are defined as 40-150 nm diameter vesicles of endocytic origin, similar in size to viruses, with a bilayered lipid membrane, a cup shaped morphology, and densities ranging between 1.13-1.19 g/mL (Silva 2015).

Exosomes have recently emerged as important mediators in cell communication due to their enriched content in genetic material like DNA, mRNA, and non-coding RNAs such as microRNAs (miRNA). (Silva 2015) MicroRNAs are small (19-24bp) endogenous RNAs that regulate gene expression at the posttranscriptional level by targeting mRNA transcripts. (Silva 2015)

The biogenesis of exosomes, which involves the endosomal compartment, sets them apart from other extracellular vesicles (EV). (Whiteside 2016) Their molecular profile partly, but not completely, resembles that of the parental cell. Exosomes are composed of a lipid bilayer and at any given point can contain all known molecular constituents of a cell. (Kalluri 2016) Similarities in the molecular and genetic profile of the parent cell are usually present, and this has given rise to the concept of exosomes as putative tumor biomarkers. (Whiteside 2016)

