5.4 Method for Assigning Subjects to Treatment Groups

Randomization of 1:1 will be assigned at the time of accrual. At the outpatient offices of the Department of Otolaryngology- Head and Neck Surgery, subjects will be randomly assigned to receive either a metformin or placebo. The Division of Biostatistics will generate the randomization schedule prior to the initiation of the study using the method of random permuted blocks. Randomization assignments will be loaded into a REDCap

database, and assignments will be accessed by the study coordinator using the REDCap randomization facility.

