7.0 STATISTICAL PLAN

7.1 Sample Size Determination

The sample size was chosen to have adequate precision for estimating the effect size comparing groups with respect to change from pre-resection to post-resection. From data in Bikas et al, we estimate that the standardized effect size for comparing change from pre-resection to post-resection between groups will be at least 0.78 standard deviations. For a 95% confidence interval to have half-width of 0.78 SDs, 14 patients per group are required. Allowing for 10% attrition, we will recruit and randomize 32 patients (16 per group).

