7.2 Statistical Methods

The primary objective of the study is to estimate the impact of metformin on change in complete blood count. Longitudinal measures of CBC will be modeled using mixed effects linear regression. Outcomes will be transformed as necessary (e.g., log transformed) prior to analysis. Fixed effects will include time (Pre-resection, Post-resection, 3 months post-resection, 6 months post-resection, 12 months post-resection), treatment (metformin vs. control) and treatment by time interaction. We will use a linear contrast to test the null hypothesis that change from pre-resection to post-resection is the same in the control and metformin groups. Secondary analyses will compare groups with respect to change from pre-resection to each of the follow-up times. Components of complete blood count will be analyzed with similar models.

Other longitudinally measured continuous outcomes will be modeled using mixed effects linear regression and longitudinally measured binomial and ordinal outcomes will be modeled using generalized linear mixed effects regression.

7.3 Subject Population(s) for Analysis:

All randomized participants with any data will be included in the analysis as randomized. Missing outcome data will not be imputed.

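### The Section 7.2 model contains no measure of radiation exposure, so an observed imbalance in I-131 activity would shift the CBC estimate and the interval may be wider than necessary

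*Combined protocol and SAP*

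**What the plan says.** Section 7.2 models repeated blood counts by mixed-effects linear regression. Its fixed effects are time, "treatment (metformin vs. control) and treatment by time interaction". The primary contrast compares the arms on change from the pre-resection to the post-resection sample. No baseline or exposure covariate is listed.

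Section 5.4 allocates 1:1 at accrual "using the method of random permuted blocks" and names no stratification factor. Sections 4.1 and 4.2 restrict neither I-131 activity nor TSH preparation. Appendix A has a row for radiation treatment but none for recording either factor.

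The background in Section 1.2 lists several influences on marrow suppression, among them "the total cumulative prescribed activity of I-131". It calls the salivary effect dose-related. On preparation it is more guarded, describing transient count effects "which some studies have shown to be less evident with an rhTSH preparation as compared to traditional TH withdrawal". It cites guideline activities by risk group, starting from "a minimum activity of 30-100 mCi" and reaching 200 mCi in the higher range.

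Section 7.1 sets the size by precision: "For a 95% confidence interval to have half-width of 0.78 SDs, 14 patients per group are required". With 10% attrition this becomes 16 per group. Under Section 5.9 patients are blinded, but the principal investigator and the care providers who make assessments are not.

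**The concern.** Metformin is being tested for its power to reduce the effect of a radiation exposure, and that exposure may differ between patients. The eligibility criteria already exclude marrow-affecting disease and drugs, but the exposure itself is neither balanced by design nor used in the analysis. In a trial of 32, one arm may by chance receive lower activities, and part of any apparent protection could then be a difference in exposure. Because the investigator is unblinded, an adjustment chosen after the data are seen would not settle that question; one chosen beforehand would. There is also a possible loss of precision: outcome variation that activity could explain stays in the residual, and precision is what Section 7.1 is built on.

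**Working it through.** **Inputs.** From Section 7.1: 95% interval, target half-width 0.78 SD of change, 14 evaluable and 16 randomised per arm. (The schema in the Study Summary shows 30 per arm; I use the 7.1 figures.) R², the share of within-arm variance in change explained by the covariate, is not in the documents. I assume 0 to 0.4.

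**1. The plan's own figure.** Half-width = t(0.975, 2n−2) × √(2/n).
- n = 14: 2.056 × 0.378 = 0.777
- n = 13: 0.810

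So 14 is the smallest n that meets 0.78. Then 14/0.9 = 15.6, rounded up to 16 per arm and 32 in total. The stated size reproduces.

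**2. Size of a chance imbalance.** The between-arm difference in a standardised covariate has SD √(2/n): 0.378 at 14 per arm and 0.354 at 16. At 14 per arm it exceeds 0.5 covariate SDs with probability 2 × [1 − Φ(0.5/0.378)] = 0.19; at 16 the figure is 0.16.

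**3. Shift in the unadjusted contrast, given such an imbalance.** Shift = √R² × 0.378 for an imbalance of one SD of its chance distribution, at 14 per arm.
- R² = 0.1: 0.316 × 0.378 = 0.12 SD, 15% of 0.78
- R² = 0.2: 0.447 × 0.378 = 0.17 SD, 22%
- R² = 0.4: 0.632 × 0.378 = 0.24 SD, 31%

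**4. Behaviour over repeated trials.** In 8,000 simulated trials at each of five R² values from 0 to 0.3, with 14 per arm and no true effect, the unadjusted estimate averaged about zero and its 95% interval covered 94.6% to 95.0%.

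**5. Half-width after adjustment.** With p covariates and N = 28, half-width = t(0.975, 26−p) × √[(2/14)(1−R²)] × √[(N−3)/(N−p−3)]. The last factor is the average cost of chance imbalance. The unadjusted value is 0.777.

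| R² | Activity only | Activity and TSH preparation |
|---|---|---|
| 0 | 0.794 (+2.3%) | 0.813 (+4.7%) |
| 0.1 | 0.754 (−3.0%) | 0.772 (−0.7%) |
| 0.2 | 0.711 (−8.5%) | 0.727 (−6.4%) |
| 0.4 | 0.615 (−20.8%) | 0.630 (−18.9%) |

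In the last column R² is the share explained by both covariates together. Break-even R² at 14 per arm is about 0.04 for activity alone and 0.09 for both. At 16 per arm it is about 0.04 and 0.07.

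**6. Form of the covariate term.** In one simulated data set (28 patients, five times, random intercept, no missing values), adding the covariate as a main effect left the change contrast at 0.098. Adding covariate by time moved it to 0.119. A main effect alone does nothing for a contrast of change when data are complete.

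**The case against.** The strongest reply is that nothing here is invalid. Randomisation keeps the unadjusted contrast unbiased, and its interval already allows for chance imbalance. A reader might infer from step 3 that the primary estimate is biased or that the interval understates its uncertainty; step 4 shows neither. The 0.12 to 0.24 SD shift is part of the sampling error inside the 0.777, and it matters only conditionally, once an imbalance has been seen. This stands.

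A reader might also infer that the interval is certainly wider than it need be. That depends on an R² the documents do not supply, and for the primary contrast it may be small. If post-resection means the postoperative sample before study drug, activity cannot affect it. If it means the sample within three days after RAI (Section 2.1), Section 1.2 puts the nadir of leukocytes and platelets at one to two months. This also stands, and is why the time points must be settled first.

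Two further limits stand. The case for TSH preparation rests on a hedged sentence about some studies. The 30 to 200 mCi span joins guideline minimum ranges for different risk groups and does not describe this centre's patients.

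The last objection concerns the remedy. Allocation is at accrual, which can precede surgery, and prescribers may know it. Activity fixed later could in principle be influenced by arm, and adjusting for it could introduce bias. This is answered by using planned activity recorded before allocation where it exists. Otherwise the value should be fixed before the first study dose and reported by arm, although with 14 to 16 per arm such a comparison can detect only a large difference.

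**Conclusion.** The point holds as a missed, inexpensive improvement, not as an error that invalidates the analysis. The protocol itself names cumulative prescribed activity as an influence on marrow suppression, and the plan neither balances nor uses it. At 14 per arm, a typical imbalance would move the observed estimate by 15% to 31% of the planned 0.78 SD if R² is 0.1 to 0.4. Adjusting for activity alone improves precision if R² exceeds about 0.04. Both statements rest on the assumed R² and on a post-RAI time point at which activity can act. The documents do not support giving TSH preparation the same standing.

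**What to change.** 1. Define each time point in Section 7.2 relative to RAI, including which sample the primary contrast calls post-resection.
2. Prespecify a CBC analysis that adds planned I-131 activity, continuous, with its interaction with time. Report the unadjusted estimate beside it, and state in advance which of the two is the headline result.
3. Record planned activity before randomisation where it is known, otherwise before the first study dose. Tabulate it by arm, because the investigator and care providers are unblinded.
4. Record TSH preparation, report it by arm, and use it only in a sensitivity analysis.
5. For the xerostomia scores, adjust for activity only; the documents link salivary effects to dose but not to preparation.

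The cost is a few lines of analysis text and two values on the case report form. The statistical downside, if the covariates explain nothing, is a half-width of 0.794 instead of 0.777 with activity alone (about 2%), or 0.813 where both are used (about 5%). Either would slightly miss the 0.78 target at 14 evaluable per arm.

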Schema	
32 patients with thyroid cancer who undergo primary surgical resection and subsequently require RAI treatment.
 
Preoperative blood and saliva
 
Thyroidectomy
 
Recovery for approx 6-8 weeks
 
Postoperative Pretreatment Metformin Blood and Saliva
  <pre> graph TD A[Postoperative Pretreatment Metformin Blood and Saliva] --> B[Randomized Metformin treatment* (n=30) or placebo treatment (n=30) 1 wk] B --> C[Post-metformin or placebo Pre-RAI Tx blood and saliva] C --> D[RAI Tx] D --> E[Post RAI blood and saliva] E --> F[Metformin or placebo Treatment** 2 wks] F --> G[Post-RAI Tx blood sample q 3mo x 12 mos] </pre> 
*Metformin (500 mg/day for 3 days followed by 500 mg twice daily for 3 days followed by 1000 mg twice daily from day 6 until RAI tx)
 
**Metformin (1000 mg twice daily for two weeks following RAI tx)

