2.0 STUDY OBJECTIVES

1. To estimate the capacity of metformin to mitigate radioactive iodine therapy-induced myelosuppression as assessed by CBC
2. To assess the capacity of metformin to mitigate known side effects of radioactive iodine therapy including xerostomia, xerophthalmia, and dysgeusia as assessed by standardized questionnaire
3. To analyze changes in serum and salivary exosome profiles following a trial of metformin administration in patients receiving radioactive iodine treatment

2.1 Primary Objective:

We have chosen complete blood count (CBC) as our primary endpoint and serum and salivary exosome profiles as secondary endpoints. To evaluate if treatment with metformin inhibits RAI-induced myelosuppression and induces faster recovery of white blood cell count to baseline values, the blood counts will be compared in the pre- and post-treatment samples. Blood parameters will include hemoglobin, red blood-cell count, white blood-cell count, absolute neutrophil count, absolute lymphocyte count, and

Thomas
Jefferson
University

platelet count. Blood and salivary samples will be drawn before surgery, before and immediately after treatment with metformin and RAI, and every three months thereafter for one year.

All blood samples will be taken by a phlebotomist or trained personnel. A baseline blood sample, consisting of two tubes of 1 cc of whole blood each, will be drawn before thyroidectomy as part of standard procedure at patients' pre-operative testing appointment. Patients will recover for a period of 6-8 weeks and identical samples will be drawn within 72 hours of starting metformin. Then samples will be drawn within three days before and within three days after RAI treatment, at the conclusion of metformin treatment, and every three months thereafter for one year. Blood parameters will include hemoglobin, red blood-cell count (RBC), white blood-cell count (WBC), absolute neutrophil count (ANC), absolute lymphocyte count (ALC), and platelet count. Assays will also be conducted on samples to assess metformin-induced changes in serum and salivary cytokines and growth factors, erythrocyte sedimentation rate (ESR), exosome evaluation, and metabolomics profile. 5 cc samples of patient saliva will be collected in specimen cups.

2.2 Secondary Objective:

- Assess safety and tolerability of metformin treatment in subjects undergoing RAI treatment for differentiated thyroid cancer

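### Section 7.2 measures all CBC change from the single pre-resection value and leaves the planned post-operative, pre-drug CBC out of the baseline; using both would probably tighten the primary interval, by an amount the documents cannot fix

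*Combined protocol and SAP*

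**What the plan says.** Section 7.2 fits a linear mixed model to CBC with five time levels: pre-resection, post-resection, and 3, 6 and 12 months post-resection. The primary analysis is a "linear contrast to test the null hypothesis that change from pre-resection to post-resection is the same in the control and metformin groups". The secondary analyses also measure change from pre-resection, at each follow-up time.

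Section 2.1 plans more draws than that. After the sample taken before thyroidectomy, "Patients will recover for a period of 6-8 weeks and identical samples will be drawn within 72 hours of starting metformin", with the same blood parameters. The schema in the Study Summary shows this draw as "Postoperative Pretreatment Metformin Blood and Saliva", ahead of the randomized treatment week. Section 3.1 likewise lists a post-operative draw before metformin. Further draws follow shortly before RAI, shortly after RAI, at the end of study drug, and every three months for a year.

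Section 7.1 sizes the trial on precision: "For a 95% confidence interval to have half-width of 0.78 SDs, 14 patients per group are required". It allows 10% attrition and randomizes 16 per group.

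**The concern.** Two CBCs precede any study drug, but only the older serves as a reference. A single CBC carries day-to-day and laboratory variation, and a change score takes that in full. The unused draw is closer to RAI and follows surgery. For patients enrolled after surgery, section 4.1 (item 4) accepts pre-operative laboratory values already on file, so the unused draw is their only baseline CBC collected within the trial.

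The mixed model does not recover this information by itself. With a full treatment-by-time interaction and complete data, the pre-to-post contrast is the difference between arms in mean change, whatever other time levels are present. The contrast, or the constraint on baseline means, has to change.

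What is at stake is interval width, the one quantity on which the trial is sized.

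**Working it through.** **Inputs from the documents.** Two-sided 95% interval, target half-width 0.78 SD, 14 evaluable per group, 10% attrition (7.1); 1:1 allocation (5.4). Section 7.1 does not say which SD it means. I read it as the SD of change from pre-resection, because 7.1 describes a "standardized effect size for comparing change from pre-resection to post-resection between groups will be at least 0.78 standard deviations".

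**Inputs assumed.** Within-patient correlations and relative SDs of the draws. The documents give none, so a range is shown.

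**Step 1: the plan's own figure.** Half-width = t(0.975, 2n−2) × √(2/n).
- n = 13: 0.810
- n = 14: 0.777, which meets 0.78
- Attrition: 14/0.9 = 15.6, rounded up to 16 per group, 32 in total

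The stated sample size reproduces.

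**Step 2: equal SDs and a common correlation r.** Let B1 be the pre-operative value, B2 the post-operative pre-dose value and Y the post-RAI value, each with variance s².
- Var(Y − B1) = 2s²(1 − r)
- Var(Y − (B1+B2)/2) = 1.5s²(1 − r)
- Ratio of interval widths = √(1.5/2) = 0.866, so 13.4% narrower for any r
- Half-width at 14 per arm: 0.777 × 0.866 = 0.673, in SDs of Y − B1
- Same precision from one baseline: 14/0.75 = 18.7 per arm

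A simulation at r = 0.6 with 14 per arm gave 13.3%.

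**Step 3: unequal correlations, equal SDs.** Compare 1 + (1 + r12)/2 − r1y − r2y with 2(1 − r1y).

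| r12 | r1y | r2y | Width, both draws v pre-operative only |
|---|---|---|---|
| 0.5 | 0.5 | 0.7 | 25.8% narrower |
| 0.6 | 0.6 | 0.75 | 25.0% narrower |
| 0.6 | 0.7 | 0.6 | 8.7% narrower |
| 0.7 | 0.5 | 0.5 | 7.8% narrower |
| 0.8 | 0.6 | 0.6 | 6.5% narrower |
| 0.9 | 0.6 | 0.6 | 3.2% narrower |
| 0.6 | 0.7 | 0.5 | no change |
| 0.9 | 0.6 | 0.5 | 3.1% wider |
| 0.8 | 0.7 | 0.55 | 4.1% wider |

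Setting the two variances equal gives the break-even: r1y − r2y = (1 − r12)/2. Equal weights lose only when the pre-operative draw is the better predictor by more than this: 0.2 at r12 = 0.6, 0.1 at 0.8, 0.05 at 0.9.

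**Step 4: unequal SDs.** With all correlations 0.6 and the pre-dose SD 1.3 times the others, the variance is 1 + 1.0625 − 1.38 = 0.6825, against 0.8. The interval is 7.6% narrower.

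**Step 5: baseline adjustment instead of change.** Under equal correlations the residual variance is 1 − r² with one baseline and 1 − 2r²/(1 + r) with two. The second draw then narrows the interval by 2.7% (r = 0.3), 5.7% (0.5), 8.9% (0.7) or 11.9% (0.9). These figures ignore the small cost of estimating the coefficients.

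**The case against.** The strongest reply is that nothing here is wrong. A single pre-treatment reference is unbiased under randomization, and the stated precision target is met. That stands. A reader might infer that the primary analysis is biased or the sample size miscalculated; the documents support neither.

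A reader might also take 13% as the general gain. It needs equal SDs and correlations. The two draws are at least 6–8 weeks apart with surgery between them, and RAI separates both from the outcome. They may well correlate more with each other than with the outcome, which gives smaller gains.

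The time labels raise a prior difficulty. Read literally, the pre-dose draw is itself a post-resection sample. If it were the post level in 7.2, it could not also be a baseline. But that contrast would compare two drug-free samples and could not address RAI-induced myelosuppression, the primary objective in 2.1. So this reading does not rescue 7.2; it shows that the labels must be settled first.

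Nor is the change wholly free. The averaged reference mixes pre- and post-surgical levels, which blurs the recovery-to-baseline aim in 2.1. The 72-hour window in 2.1 does not itself say before the first dose, although 3.1 and the schema do. Appendix A has no separate column for this draw. Under 6.4.1, CBCs depend on patients having prescribed draws done and results forwarded, so its completeness is uncertain.

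**Conclusion.** The point holds as a worthwhile precision gain. Section 7.2 omits from the baseline a drug-free CBC that the protocol already plans in both arms. Randomization is at accrual (5.4), so this draw may follow it, but no drug has yet been taken and expected values are equal between arms. Any effect of surgery on counts is likewise expected to be equal.

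For equal weights against change from pre-resection alone, the gain is about 13% under equal SDs and correlations. It runs from about 0 to 26% in plausible cases, with a loss of about 3–4% in the two adverse cases tried. That loss requires the older, pre-surgical draw to predict the outcome clearly better than the draw taken just before dosing, which the timing makes unlikely. If the analysis adjusts for baseline, the second draw adds about 3–12% under equal correlations. All these figures assume that the primary post level is a post-RAI draw.

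**What to change.** In section 7.2:

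1. Name each time level by its draw in 2.1 and tie it to RAI. State which post-RAI draw is the primary post level.
2. Add the post-operative pre-dose CBC as a second drug-free level. Do not pool the draw shortly before RAI with these two, since study drug has by then been started.
3. Preferably constrain the arm means to be equal at both drug-free levels in the mixed model, and state the covariance structure. The data then set the weights, and a patient missing one draw still contributes the other. A contrast of −1/2, −1/2, +1 is a simpler alternative, but has the fixed-weight risk shown above.
4. Name the reference for any recovery-to-baseline summary separately; it can remain the pre-operative value.

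Elsewhere, state in 2.1 that this sample is taken before the first dose, and reconcile Appendix A with 2.1 so that the draw appears there.

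The cost is a few sentences of protocol and SAP wording and a different model specification. No patients, visits or samples are added beyond those in 2.1.
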